Cover page

Mitigation of radiation pneumonitis and fibrosis

ClinicalTrials.gov Identifier: NCT01754909

Most recent IRB approval Nov 13, 2017

Statistical methods plan

Power analysis for aim 1

For the RP endpoint, at an 11% rate of clinical RP, and an 80% mitigation effect, 97 subjects are needed per arm for type 1 error of 0.05 and a power of 0.80. The 11% and 80% figures are based on our retrospective studies. Only 49 are needed per arm for a baseline clinical RP rate of 20%. We plan for 200 subjects because there is variability in the rate of RP, and because we cannot be certain about the magnitude of efficacy of enalapril.

control	%difference	treatment	n/arm	total n
11%	50%	6%	306	612
11%	60%	4%	199	398
11%	70%	3%	136	272
11%	80%	2%	97	194
11%	90%	1%	70	140
20%	50%	10%	155	310
20%	60%	8%	101	202
20%	70%	6%	70	140
20%	80%	4%	49	98
20%	90%	2%	36	72

For a 50% radiographic rate of RP, and a halving of this by enalapril, 45 subjects are needed per arm.

50%	50%	25%	45	90
-----	-----	-----	----	----

50%	60%	20%	30	60
50%	70%	15%	21	42
50%	80%	10%	15	30
50%	90%	5%	11	22

For the radiographic fibrosis endpoint, at a 90% fibrosis rate, 29 subjects per arm would identify a 30% reduction in radiographic fibrosis at 6 or 12 months.

Endpoint and RAS analyses

Dichotomous variables will be compared by chi-square, or Fisher's exact test, as indicated. Continuous variables will be compared by parametric or non-parametric statistics, as appropriate. Repeated measurements on the effects of enalapril and placebo on [RAS components] will be tested by a repeated measures ANOVA for continuous [RAS component] values and by a logistic type regression models [using GEE techniques for discrete [RAS component] values. In either case appropriate generalized linear models methods will be used to account for the association between repeated measurements over time on the testing procedure.] We will repeat the analysis using an appropriate regression analysis to account for possible patient factors which may influence outcome in addition to enalapril. We will also look at a model for RP and fibrosis using enalapril use and the RAS components as predictors as well as interactions between drug use and these predictors. Correlations will be made using Spearman's or Kendall correlation, as indicated. Dose modification factors (DMF) for the use of enalapril compared to placebo will not be tested since the expected radiation dose ranges will be too narrow. A more formal attempt to understand the mechanism of enalapril action on RP and fibrosis and determine if this is possibly derived through any one of the [RAS components] will use a structural equation modeling approach. This approach uses a matrix of regression coefficients from a series of regression models [of intermediate effects at the various time points to other intermediate effects at the same time point or to future intermediate or terminal effects. Using these coefficients and a postulated causal diagram which depicts which effects may be dependent on the patient history at a given time]. A final causal diagram which shows the relationship between drug, intermediate outcome and RP and or fibrosis [is constructed]. Path analysis techniques to construct the causal diagram can be constructed using the program DIGRAM (53). [This cited reference shows how this approach works by looking at causal factors for heart disease using data on behavioral factors measured at epochs in time.]

Survival analysis for aim 3

Cancer-related survival and cancer recurrence will be compared for the enalapril and the placebo groups using Kaplan-Meier statistics. [We have calculated our ability to detect significant changes in cancer recurrence rates and in cancer survival, both for improvements in cancer-related outcomes and for adverse trends. We will be able to detect significant increases in recurrence rates or mortality. Our cohort of 162 subjects showed no difference in patient survival for those on ACE inhibitor compared to those not on ACE inhibitor. We do not

expect adverse changes in recurrence rates or patient survival. A mitigation benefit by enalapril could lead to an increase in patient survival, but less than a three month increase is not likely to be detected]

Recurrence rate change	Percent chance of detection
40 to 20 %	80%
40 to 60 %	81%

Cancer median survival change, months	Percent chance of detection
18 to 21	11%
18 to 12	60%

[There are potential pitfalls in the recurrence and survival analyses. These include the effects of interim sampling for the safety analyses, and adjustments for patient and disease characteristics as well as missing data.] The interim masked safety analyses will use the O'Brien correction to take into account the multiple analyses. In our analysis of survival, we will compare the recurrence-free survival rates between the treatment arms of the study in two ways. First we will examine the rates of death or recurrence using a Cox model. In this model we will adjust for patient/disease characteristics such as site of treatment, gender, age, stage of disease at randomization, and radiation dosage. We will also compare the disease free survival probabilities at two years using techniques that we have published (52). This method allows us to deal with the partial information available in patients who do not have a potential follow-up time of two years. This approach, which is a censored data version of logistic regression, will allow us to adjust the comparisons for patient, disease, and treatment factors. We picked two years here since the empirical evidence is that the disease-free survival curves tend to flatten out at around 20 months.

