Our retrospective clinical studies show that concurrent use of ACE inhibitors reduces the occurrence of radiation pneumonitis [and fibrosis], without lowering cancer-related survival. The safe mitigation of radiation injury has been identified as a priority by the National

Cancer Institute. We will address this critical problem. We hypothesize that the occurrence of radiation pneumonitis, fibrosis, or both in patients receiving radiation for lung cancer will be decreased by the ACE inhibitor enalapril, started after irradiation.

4. STUDY DESIGN. Provide a brief description of the design of the study (multicenter, double-blind, randomized, etc.) in narrative form. Do not provide details of specific procedures in this section (see Item 9 below). Include, as needed, a discussion of the appropriateness of research methods. Describe the statistical design and required sample size. Do not indicate "N/A" for this category.

This is a prospective, double-blinded, randomized, placebo-controlled trial, in a secondary-tertiary care setting. The ZVAMC and referring VAs in VISN 12 are the main centers; the Baltimore VAMC will be added. Subjects will join this trial voluntarily, based on their planned radiotherapy for lung cancer. We will enroll 200 subjects over the five years of this study. Statistical power analysis suggests the need for 200 subjects for the clinical endpoint, and ~ 100 subjects for the radiographic endpoint.

5. SUBJECT SELECTION AND EXCLUSION CRITERIA. Provide the specific criteria for including and excluding subjects in the study. Do not indicate "N/A" for this category.

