The therapeutic risk is that of the medical care by, during, and after radiation therapy for

lung cancer. The research risk is that of the use of the study drug, enalapril or placebo, as detailed above. There is also the risk of obtaining blood for RAS studies. There is no alternative to the therapeutic risk, for subjects undergoing radiation therapy, because it is the standard of care for those subjects. The alternative to the research risk is to not participate in this study. The alternative is to undergo usual and customary care, by radiation therapy for the patient with lung cancer.

Data security and confidentiality will be maintained according to the rules of the Department of Veterans Affairs. Risks to breach of privacy and confidentiality will thereby be avoided. All data for this study will only be stored on password-protected VA computers. Data collection for complications of treatment, adverse and severe adverse events will be done by a dedicated study coordinator who will prospectively track all of the subjects of this study.

11. ANTICIPATED BENEFITS OF THE STUDY AND RISK/BENEFIT ASSESSMENT.

Describe the benefit to the subject and/or benefit to science. State if subjects will receive no benefit.

Investigational devices: Benefits of investigational device compared to benefits of alternative devices or procedures.

Subjects in this study may have a fifty percent or more reduction in the occurrence of radiation pneumonitis. Based on pre-clinical data in laboratory animals, we expect that to occur in subjects on enalapril compared to subjects on placebo. But this is not known or guaranteed, which is why this study of enalapril compared to placebo must be done. Based on extensive use of enalapril for other indications, and on our study of its congener, lisinopril, in veterans undergoing radiation therapy for lung cancer, the risks of this study related to use of study drug are small, and reasonable in relation to the anticipated benefits to subjects and others.

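### Aim 1 sample sizes fit an undeclared one-sided 0.05 test; if the primary test is two-sided, 200 subjects give about 71% power in the base case, not 80%

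*SAP*

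**What the plan says.** The SAP, Power analysis for aim 1, takes an 11% rate of clinical RP and an 80% reduction and concludes that "97 subjects are needed per arm for type 1 error of 0.05 and a power of 0.80". Its tables give sizes per arm for control rates of 11%, 20% and 50% with reductions of 50% to 90%. For the radiographic endpoint it says: "For a 50% radiographic rate of RP, and a halving of this by enalapril, 45 subjects are needed per arm". A further line gives 29 per arm for a 30% reduction in fibrosis from 90%. The reason for the total is given as "We plan for 200 subjects because there is variability in the rate of RP", together with doubt about the size of the effect.

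The SAP, Endpoint and RAS analyses, names the test: "Dichotomous variables will be compared by chi-square, or Fisher's exact test, as indicated". Protocol section 4 carries the sizes forward: "Statistical power analysis suggests the need for 200 subjects for the clinical endpoint, and ~ 100 subjects for the radiographic endpoint". Protocol section 3 states the hypothesis in one direction, that RP and fibrosis "will be decreased by the ACE inhibitor enalapril, started after irradiation". None of these places says whether the 0.05 is one-sided or two-sided.

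**The concern.** A type 1 error of 0.05 with no further word, beside a chi-square or Fisher test, will normally be read as two-sided. On that reading the stated sizes are too small for 80% power, and the shortfall falls on the scenario that set the trial size.

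Two things are at stake. First, the p-value that decides the clinical endpoint is not fixed, so the threshold could be settled after the data are seen. Second, if the test is two-sided and the result is negative, readers will judge it against 80% power that the design does not have at an 11% RP rate.

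**Working it through.** **Inputs.** From the SAP: type 1 error 0.05, power 0.80, and the control rates and reductions in its tables. An 80% reduction from 11% is 0.11 × 0.20 = 0.022 (the table prints 2%). Planned total 200; 100 per arm assumes equal allocation, as the table implies (97 per arm, 194 total).

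**Formula** (two proportions, pooled variance under the null, no continuity correction), with p̄ = (p1 + p2)/2:

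n per arm = [z_α √(2p̄(1−p̄)) + z_β √(p1(1−p1) + p2(1−p2))]² / (p1−p2)²

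**Reproducing the plan's 97.** p1 = 0.11, p2 = 0.022, p̄ = 0.066. The two roots are √0.123288 = 0.3511 and √0.119416 = 0.3456; (p1−p2)² = 0.007744; z_β = 0.8416.
- One-sided, z_α = 1.645: (0.5776 + 0.2908)² / 0.007744 = **97.4**, against 97 stated.
- Two-sided, z_α = 1.960: (0.6882 + 0.2908)² / 0.007744 = **123.8**, so 124 per arm (248 total).

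**The other rows, n per arm:**

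| Control → treated | Stated | One-sided | Two-sided |
|---|---|---|---|
| 11 → 5.5% | 306 | 308.4 | 391.6 |
| 11 → 4.4% | 199 | 200.7 | 254.9 |
| 11 → 3.3% | 136 | 137.4 | 174.6 |
| 11 → 1.1% | 70 | 70.7 | 89.8 |
| 20 → 10% | 155 | 156.6 | 199.0 |
| 20 → 8% | 101 | 102.3 | 130.1 |
| 20 → 6% | 70 | 70.3 | 89.4 |
| 20 → 4% | 49 | 49.9 | 63.6 |
| 20 → 2% | 36 | 36.3 | 46.2 |
| 50 → 25% | 45 | 45.3 | 57.7 |
| 50 → 20% | 30 | 30.2 | 38.5 |
| 50 → 15% | 21 | 21.1 | 26.9 |
| 50 → 10% | 15 | 15.1 | 19.4 |
| 50 → 5% | 11 | 11.1 | 14.2 |

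All 15 rows lie within 3 of the one-sided value, and none fits the two-sided one. At the stated sizes, power is 79.3–79.9% one-sided and 68.0–69.7% two-sided. For the base case, no two-sided variant gives 97: continuity-corrected 146, unpooled 121.0, arcsine 109.6, and 117 with the printed 2%. The fibrosis line does not discriminate: 29 fits a one-sided 90 → 63% (29.4) but also a two-sided unpooled 90 → 60% (28.8).

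**Power at 100 per arm, 11% vs 2.2%.** Power = Φ{[(p1−p2)√n − z_α × 0.3511] / 0.3456}, where (p1−p2)√n = 0.088 × 10 = 0.88.
- Two-sided: Φ[(0.88 − 0.6882)/0.3456] = Φ(0.555) = **71%**
- One-sided: Φ[(0.88 − 0.5776)/0.3456] = Φ(0.875) = **81%**

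Exact power, by enumerating both binomial distributions:

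| Test | Two-sided | One-sided |
|---|---|---|
| Chi-square | 74.3% | 85.6% |
| Fisher | 64.9% | 74.4% |

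For chi-square the gap is 11.2 percentage points: the share of base-case trials that are significant one-sided but not two-sided.

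**Other scenarios at 100 per arm (formula).**

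| Scenario | Two-sided | One-sided |
|---|---|---|
| 11 → 5.5% | 29% | 41% |
| 20 → 10% | 51% | 63% |
| 20 → 8% | 69% | 79% |
| 20 → 6% | 84% | 91% |
| 20 → 4% | 94% | 97% |
| Radiographic RP 50 → 25% | 96% | 98% |
| Fibrosis 90 → 63% | >99% | >99% |

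The reduction detectable with 80% power is 87% two-sided or 79% one-sided at an 11% baseline, and 67% or 61% at 20%.

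**The case against.** The strongest reply is that nothing has been miscalculated. The one-sided formula returns the stated sizes, and with a one-sided 0.05 test 200 subjects give 81%. A one-sided test is plausible: the protocol calls the trial phase 2 and its hypothesis is directional. That the named tests are two-sided is convention, not a statement in the documents. All of this stands, so the shortfall is conditional. But the 80% claim then depends on a choice the plan does not record. Language about both directions appears only for stopping (protocol section 12) and for aim 3, so it does not settle aim 1. Part of the protocol was not available for this check, so a declaration there cannot be excluded; the SAP's own aim 1 sections contain none.

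Second, the Fisher figures may be too pessimistic. Under the common rule of using chi-square when every expected count is at least 5 (an assumption; the SAP does not define its rule), chi-square applies in 86% of base-case trials, and power is 72.5% two-sided and 82.4% one-sided. This is fair, but the two-sided figure is still below 80%. So is the exact chi-square figure with the printed 2% rate (77.2%).

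Third, the baseline from which an 80% reduction has 80% two-sided power depends on the method: about 13.4% by formula, about 12.5% by exact chi-square or the mixed rule, and higher than 13.4% for Fisher. All exceed 11%.

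Fourth, the SAP's table already shows that smaller effects at 11% need 272 to 612 subjects. True, but the text beside it still offers uncertainty about rate and effect as the reason for 200. The protocol's benefit statement, "Subjects in this study may have a fifty percent or more reduction in the occurrence of radiation pneumonitis", rests on animal data and is not a design assumption; the 50% rows above show only what the design could detect.

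**Conclusion.** The point holds and should be fixed before unblinding. The aim 1 tables are a one-sided 0.05 calculation that is not labelled as such. If the primary test is two-sided, power in the 11%/80% base case is about 71% by formula, and 65% to 74% by exact calculation depending on the test; 80% by formula would need 124 per arm. If it is one-sided, the stated 80% is met by formula and by chi-square, but not if Fisher's test is always used (74%).

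The problem is confined to the low baseline rate and smaller effects. At 20% vs 4% and for the radiographic endpoints, 100 per arm is ample on either reading. At an 11% baseline, 200 subjects leave no allowance for an effect below about 80% on either reading; at 20% they leave some. These figures assume equal allocation, 100 evaluable subjects per arm, and a treated rate of 2.2%.

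**What to change.** Keep 200 subjects. Before unblinding, state in the SAP whether the clinical RP test is one-sided or two-sided, and name the test (or the exact rule for choosing between chi-square and Fisher). Then make the power text agree.

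- **If two-sided:** restate the tables; the four headline sizes become 124 (11%/80%), 64 (20%/80%), 58 (radiographic RP halved from 50%) and 38 (fibrosis 90 → 63%) per arm. State about 71% power for 11% vs 2.2%, and detectable reductions of about 87% at an 11% baseline and 67% at 20%. In protocol section 4, change the radiographic figure of about 100 to about 116 (2 × 58), noting that 200 subjects still cover it comfortably.
- **If one-sided 0.05 was intended:** say so beside the type 1 error, apply it in the analysis, and report that exact power at 100 per arm is about 86% with chi-square but about 74% with Fisher.
- **In either case:** say plainly that at an 11% baseline 200 subjects give no allowance for a reduction below about 80%.

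The cost is a few lines in the SAP and, if two-sided, one figure in the protocol. No extra subjects or visits are needed. If the test is two-sided, the stated power becomes less favourable.

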10. RISKS AND PRECAUTIONS. Provide a description of all risks (physical, psychological, social, legal, and/or economic) for each drug or procedure used. Indicate how risks will be minimized, including a description of procedures already being performed on the subjects for diagnostic or treatment purposes that will be used. Provide a description of these procedures. ***Distinguish risks associated with research from risks of therapies subjects would receive even if not participating in research.*** Include precautions to be taken to minimize the danger and/or pain. Provide a plan for notifying subjects of new findings that may affect their willingness to participate in the project. If there are no risks to participating in the study, this should be stated. Do not indicate "N/A" for this category.

Investigational devices: Include the risks of procedures involved in the use of investigational device and risks of investigational device compared to risks of alternative devices or procedures.

Enalapril is an angiotensin-converting-enzyme inhibitor in common use, for treatment of hypertension, kidney disease, and heart failure. It is used to lower blood pressure, and is also used in normotensive subjects with heart failure. Subjects with normal blood pressure who would use enalapril to mitigate radiation injury could develop low blood pressure which could cause dizziness and drug intolerance. This will be avoided by starting with low doses and increasing the drug dose, as tolerated. Elevation in serum potassium could occur; we will test for this in one extra blood sample, and monitor for it in subsequent usual clinical follow-up. Between 2 and 5% of subjects using enalapril could develop a cough, which resolves within a few days of stopping the drug. Intolerable cough will lead us to stop the study drug. The safety of enalapril in this use is very likely, because we have documented the safe use of lisinopril, another angiotensin-converting enzyme inhibitor and a congener of enalapril, in veterans at ZVAMC undergoing radiation therapy for lung cancer. These were subjects already on lisinopril when they underwent radiation therapy for lung cancer. We found no adverse effects of this use of lisinopril. In another study, we used captopril compared to placebo in bone marrow transplant patients, to mitigate chronic renal failure. There was no difference in drug tolerance in patients on captopril compared to those on placebo.

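### The 200 subjects are said to allow for a variable RP rate and uncertain efficacy, but they are six more than the 194 tabulated for an 11% rate and 80% reduction, so the allowance is almost nil for a lower rate or, at 11%, a weaker effect

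*SAP*

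**What the plan says.** The SAP (Power analysis for aim 1) sizes the clinical RP endpoint "at an 11% rate of clinical RP, and an 80% mitigation effect" and finds that "97 subjects are needed per arm for type 1 error of 0.05 and a power of 0.80". On the source it says: "The 11% and 80% figures are based on our retrospective studies". It then gives a more favourable case, "Only 49 are needed per arm for a baseline clinical RP rate of 20" percent, and justifies the total: "We plan for 200 subjects because there is variability in the rate of RP". Its second reason for 200 is doubt over how well enalapril works.

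The table that follows gives these totals for clinical RP:

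| Control rate | 50% reduction | 60% | 70% | 80% | 90% |
|---|---|---|---|---|---|
| 11% | 612 | 398 | 272 | 194 | 140 |
| 20% | 310 | 202 | 140 | 98 | 72 |

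Protocol item 4 (Study Design) gives the same 200 as the requirement for the clinical endpoint. Protocol item 11 (Anticipated Benefits) says: "Subjects in this study may have a fifty percent or more reduction in the occurrence of radiation pneumonitis". It bases this on animal data and adds that it is not guaranteed. The SAP's analysis section names chi-square or Fisher's exact test for dichotomous outcomes and does not say whether tests are one- or two-sided.

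**The concern.** A reader of the rationale sentence would take 200 to be the base-case requirement plus a margin for a different RP rate and a weaker effect. Set against the table, the margin over the base case is 200 − 194 = 6 subjects, or 3.1%. The next weaker effect at 11% (a 70% reduction) needs 272, already 72 more than planned.

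At stake is how the primary clinical result is read. If the trial is described as having room for uncertain efficacy, a non-significant result can look more informative than it is. At an 11% rate, a halving of RP would be missed more often than detected.

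**Working it through.** **Inputs.** Control rates of 11% and 20%, the reductions, alpha 0.05 and power 0.80 come from the SAP. The treated rate is control × (1 − reduction), unrounded. I take 100 per arm; 1:1 allocation is implied by the table's equal arms but is not stated.

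**Step 1: reproduce the table.** Pooled two-proportion formula without continuity correction:

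n per arm = [z_α·s0 + z_β·s1]² / d², where d = p1 − p2, p̄ = (p1 + p2)/2, s0 = √(2p̄(1 − p̄)), s1 = √(p1(1 − p1) + p2(1 − p2)), z_β = 0.8416.

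Base case: p1 = 0.11, p2 = 0.022, d = 0.088, p̄ = 0.066, s0 = 0.3511, s1 = 0.3456.
- One-sided (z_α = 1.6449): (0.5775 + 0.2909)² / 0.007744 = 97.4, rounded up to 98. The SAP has 97.
- Two-sided (z_α = 1.9600): (0.6882 + 0.2909)² / 0.007744 = 123.8, rounded up to 124.

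One-sided, all 15 clinical and radiographic RP rows come out within 3 per arm (for example 309 against 306, 157 against 155, 46 against 45). Two-sided, none does (392, 199 and 58 for the same rows). A continuity correction does not fit the base case either (120 one-sided, 146 two-sided).

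**Step 2: power with 100 per arm.** Power = Φ[(d√100 − z_α·s0) / s1].
- 11%, 80% reduction, one-sided: (0.88 − 0.5775)/0.3456 = 0.875, power 80.9%. Two-sided: (0.88 − 0.6882)/0.3456 = 0.555, power 71.1%.
- 11%, 50% reduction (p2 = 0.055, s0 = 0.3891, s1 = 0.3871), one-sided: (0.55 − 0.6400)/0.3871 = −0.232, power 40.8%. Two-sided: (0.55 − 0.7626)/0.3871 = −0.549, power 29.1%.

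| Control rate | Reduction | SAP total | Power with 200, one-sided | Two-sided |
|---|---|---|---|---|
| 11% | 80% | 194 | 81% | 71% |
| 11% | 70% | 272 | 68% | 56% |
| 11% | 60% | 398 | 54% | 42% |
| 11% | 50% | 612 | 41% | 29% |
| 20% | 80% | 98 | 97% | 94% |
| 20% | 60% | 202 | 79% | 69% |
| 20% | 50% | 310 | 63% | 51% |

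Exact enumeration at two-sided 0.05 gives 74.3% (chi-square) and 64.9% (Fisher) for the base case, and 29.8% and 21.3% for a 50% reduction at 11%.

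**Step 3: how far the margin stretches.** The smallest reduction with 80% power is about 79% at an 11% rate and 61% at 20% one-sided, or about 87% and 67% two-sided. With an 80% reduction, one-sided power stays at 80% only while the control rate is at least about 10.7%. The documents give no clinical RP rate below 11%; as assumptions, 9% and 8% with an 80% reduction give 73% and 68% one-sided (62% and 56% two-sided).

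**Step 4: losses.** Every tabulated total is exactly twice the number per arm, so nothing is added for losses. The documents give no loss rate. As assumptions, losing 5%, 10% or 20% of both arms leaves base-case power of 79%, 77% or 73% one-sided.

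**The case against.** The strongest reply is that the rationale sentence follows directly on the 49-per-arm figure for a 20% rate. Read in order, the SAP may be saying that it takes 200 rather than 98 because the rate could be 11% rather than 20%. This stands in part. The planned 200 meets five of the ten clinical rows (194, 140, 140, 98, 72) and misses a sixth (202) by two. A reader might infer that no allowance exists at all; that goes too far, since there is real slack towards a higher rate. It does not extend to a lower rate, nor to an effect weaker than 80% at 11%, and uncertain efficacy is one of the two reasons the sentence gives.

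Nor is anything hidden or miscalculated. The 272, 398 and 612 rows are printed beside the sentence. The fault lies in the justification.

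Two further readings are tempting and unsupported:
- That the 50% in protocol item 11 conflicts with the SAP's 80%. Item 11 describes 50% or more, in a benefit narrative. It is a lower end, and 80% lies within it.
- That a smaller effect is the likelier case because of the source population. Protocol item 10 says "These were subjects already on lisinopril when they underwent radiation therapy for lung cancer", whereas here drug starts between a day and 30 days from the beginning of radiotherapy. But that is a safety paragraph. It is not identified as the source of the 80%, and no passage compares effect size by start time.

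**Conclusion.** The point holds in a limited form. The six subjects above the base case give almost no protection if the RP rate is below 11%, or if the reduction at 11% is below 80%. At a 20% rate there is slack for reductions of about 61% or more one-sided (67% two-sided), but a 50% reduction still has only 63% power (51% two-sided).

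The power figures assume 100 analysed per arm and a single test at 0.05. The one-sided convention is inferred from the table's reproducing that way and no other way tried. If the trial is analysed two-sided, the base case itself has about 71% power with 200 subjects, not 80%. A reader might also infer that a null result will be taken as evidence against enalapril. The documents do not say how non-significance will be read, so the case for the change is to prevent that reading.

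**What to change.** Change wording only, in this order.

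1. State in the SAP whether the clinical RP test is one- or two-sided at 0.05. The power statement depends on it.
2. Replace the rationale sentence with what 100 per arm delivers, using the figures for the chosen test:
   - One-sided: at an 11% rate, power is 81/68/54/41% for reductions of 80/70/60/50%; at 20%, 79/63% for reductions of 60/50%. The smallest reduction with 80% power is about 79% at 11% and 61% at 20%.
   - Two-sided: 71/56/42/29% at 11% and 69/51% at 20%. The smallest reduction is about 87% and 67%.
3. Add that no allowance is made for discontinuation of study drug or for non-evaluable subjects.
4. Report the RP effect with a confidence interval that matches the test: 95% for a two-sided 0.05 test, or 90% (equivalently a one-sided 95% bound) for a one-sided one. Quoting 80% base-case power beside a two-sided 95% interval would mix the two conventions.
5. State that a non-significant result does not by itself exclude a 50% reduction, the lower end of what protocol item 11 anticipates.
6. Carry the same statement into protocol item 4.

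The cost is an amendment to the text, with no added enrolment or procedures. The downside is that the stated power becomes less favourable.

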The study drug, enalapril or placebo, will be in addition to usual clinical care of subjects undergoing radiation therapy for lung cancer. Enalapril, or placebo, will be given orally, started within a day to up to 30 days of the beginning of the radiation treatments. They will be enrolled at the start of radiation therapy (RT), stratified for cancer stage, then randomized to enalapril or identical-appearing placebo. Randomization will be done by the Department of Biostatistics, Medical College of Wisconsin, using random number tables; the center pharmacies will be notified of the assignment to enalapril or placebo. There will be no stratification by age, gender, lung cancer histology, or use of chemotherapy since these do not have a consistent relation with the occurrence of RP. There is no stratification by center. Study drug is obtained from Expert Pharmacy Inc, with identical appearing enalapril and placebo tablets. It is held in the VA research pharmacy at Milwaukee, in a restricted access area under the aegis of the research pharmacist. It will be sent to patients at the Baltimore site upon their enrollment. The study drug dose will be

2.5 mg to start, and will be increased in increments of 2.5 mg to 10 mg per day, as tolerated. Clinical follow up of study subjects will be identical to that of subjects undergoing radiation therapy for lung cancer but who are not participating in this study, with the addition of four blood samples. One blood sample one week after starting the study will be to check for adverse effects of the study drug. Three more blood samples will be obtained for renin-angiotensin system (RAS) assays, done on three blood samples from each subject, at the start of the study, at 3 weeks after the start, and at the end of radiation therapy. Each of these four research-related blood samples will be approximately one teaspoon of blood obtained by venipuncture. Compliance is assessed by monitoring the requests for study drug refills. It will be verified at the end of the study by the elevation in plasma renin in subjects on enalapril compared to those on placebo. Study subjects will be monitored for adverse effects of study drug. The development, or not, of radiation pneumonitis and fibrosis will be assessed in the study subjects, as part of ongoing regular care, as are the periodic radiographic imaging and lung function testing. Quality of life will also be assessed.

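### Randomisation is stratified by cancer stage, but the test named for the pneumonitis and fibrosis endpoints ignores stage, and the regression repeat does not name it

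*SAP*

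**What the plan says.** - **Design.** Protocol section 9 (Procedures) has subjects "stratified for cancer stage, then randomized to enalapril or identical-appearing placebo". Age, gender, histology and chemotherapy are left out of the stratification "since these do not have a consistent relation with the occurrence of RP"; centre is also left out. The number and definition of the stage groups are not given.
- **Main test.** SAP, Endpoint and RAS analyses: "Dichotomous variables will be compared by chi-square" or Fisher's exact test. No stratified version is mentioned. Grade 2 or greater clinical RP, radiographic RP and radiographic fibrosis all fall under this sentence.
- **Regression.** The same section adds: "We will repeat the analysis using an appropriate regression analysis to account for possible patient factors which may influence outcome". The factors are not listed. A further model for RP and fibrosis names only enalapril use, the renin-angiotensin (RAS) components and their interactions.
- **Aim 3.** The SAP's survival section lists "stage of disease at randomization" among the Cox model covariates. It is the only analysis that names stage.
- **Size.** Protocol section 4: "We will enroll 200 subjects over the five years of this study". The SAP's power section explains: "We plan for 200 subjects because there is variability in the rate of RP", and adds that the efficacy of enalapril is uncertain.

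**The concern.** The design controls one factor, and the test that will decide the primary outcome does not use it. The reason given for leaving other factors out suggests, without saying so, that stage was kept because it may be related to RP. If so, stratified allocation removes the between-stage part of the variation from the treatment comparison, while the plain chi-square still counts that part as noise. The test is then conservative and loses some power. If allocation is not tightly balanced within stage, the chi-square keeps its size but carries the extra variation, and power is again lost.

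This affects efficiency and pre-specification. It does not create a false-positive risk. It is worth attention because clinical RP events will be few and power is thin in some of the scenarios the plan lists. In addition, the covariates of the adjusted RP analysis, and its standing relative to the unadjusted one, are still open.

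**Working it through.** **Inputs from the documents.** 200 subjects, taken as 100 per arm; type I error 0.05, sidedness not stated. Clinical RP is 11% with an 80% reduction (2.2% on enalapril), or 20% with a 50% reduction. Protocol section 11 also speaks of a "fifty percent or more reduction in the occurrence of radiation pneumonitis". Radiographic RP is 50%, halved. Fibrosis is 90%, cut by 30%.

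**Assumptions.** RP rates by stage, the number and size of strata, and the allocation method within strata.

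**1. Reproducing the plan's sample size.** The pooled-variance formula at 80% power is

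n per arm = [zα√(2p̄q̄) + zβ√(p1q1 + p2q2)]² / (p1 − p2)².

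For 11% versus 2.2%, p̄ = 0.066, √(2p̄q̄) = 0.3511 and √(p1q1 + p2q2) = 0.3456.

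- One-sided: (1.645 × 0.3511 + 0.842 × 0.3456)² / 0.088² = 97.4. The plan has 97.
- Two-sided: (1.960 × 0.3511 + 0.842 × 0.3456)² / 0.088² = 123.8.

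For 50% versus 25% the same formula gives 45.3 one-sided and 57.7 two-sided; the plan has 45. The plan's figures therefore match a one-sided test, so results below are given both ways.

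**2. Expected events.** 100 × (0.11 + 0.022) = 13.2 clinical RP events in all.

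**3. Why the unstratified test is conservative.** With exact balance within stage, the true null variance is the within-stage variance, but the chi-square uses the total. Take stage rates of 4% and 30% in groups of 146 and 54.

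- Overall rate: (146 × 0.04 + 54 × 0.30)/200 = 11.02%.
- Within-stage variance: 0.73 × 0.04 × 0.96 + 0.27 × 0.30 × 0.70 = 0.0847.
- Total variance: 0.1102 × 0.8898 = 0.0981.
- Ratio 0.864, so the true two-sided size is about 2[1 − Φ(1.96/√0.864)] = 3.5%. Simulation gives 3.6%, against 4.8% for the stratified test.

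**4. Power by simulation.** 400,000 trials per scenario, 100 per arm, Pearson z against Cochran-Mantel-Haenszel (CMH) z, no continuity correction, critical values 1.96 and 1.645. There are two strata of 100, except for 4/30% (146 and 54). Balanced means exact halves within each stratum; simple means binomial(0.5). Each cell shows unstratified vs CMH, in %.

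| Scenario (control rates by stage) | Allocation | Two-sided | One-sided |
|---|---|---|---|
| RP 11% cut by 80%, 5.5/16.5% | balanced | 74.5 vs 75.1 | 85.8 vs 85.8 |
| | simple | 74.9 vs 75.1 | 84.6 vs 84.8 |
| RP 11% cut by 80%, 4/30% | balanced | 75.6 vs 78.9 | 86.7 vs 87.0 |
| | simple | 75.2 vs 77.7 | 84.8 vs 86.7 |
| RP 20% halved, 10/30% | balanced | 51.9 vs 53.2 | 64.1 vs 65.7 |
| | simple | 51.4 vs 52.7 | 63.9 vs 65.3 |
| Radiographic RP halved, 40/60% | balanced | 96.1 vs 96.3 | 98.1 vs 98.2 |
| Radiographic RP halved, 30/70% | balanced | 96.8 vs 97.5 | 98.5 vs 98.9 |
| | simple | 96.0 vs 97.4 | 98.1 vs 98.8 |
| Type I error, both arms 4/30% | balanced | 3.6 vs 4.8 | 3.9 vs 5.0 |
| | simple | 5.0 vs 5.0 | 5.1 vs 5.1 |

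Fibrosis at 85/95% shows no gain (99.7 vs 99.7 two-sided). At the same threefold gradient, the gain is larger for 20% halved (1.3 to 1.6 points) than for 11% cut by 80% (0 to 0.6).

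**5. Cost if stage is unrelated to RP** (11% cut by 80%). With two balanced strata, power is unchanged: 74.4 vs 74.4 two-sided, 85.5 vs 85.5 one-sided. Under simple allocation CMH loses:

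| Strata | Two-sided loss, points | One-sided loss, points |
|---|---|---|
| 2 | 0.5 | 0.3 |
| 4 | 1.0 | 0.8 |
| 10 | 2.5 | 1.9 |
| 20 | 5.3 | 3.8 |

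**The case against.** An unstratified test after stratified randomisation is valid, and choosing CMH is a matter of efficiency. No document says that stage predicts RP; it may have been balanced for the Aim 3 outcomes, where it is named. If stage is unrelated to RP, the stratified test gains nothing and can lose power when there are many strata, and the number of strata is not stated. The largest gain in the table (3.3 points) needs a 7.5-fold gradient, a two-sided test and exact balance. Part of it is discreteness: it is 2.0 points at a critical value of 1.9 and 2.2 at 2.0. At the one-sided level that matches the plan's sample sizes, the same case gains 0.3. The regression sentence is broad enough to include stage.

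Most of this stands as a limit on size. The gain is assumption-based and often small, and stratification does not repair power of 52% to 66% in the 20%-halved case. Two parts do not dispose of the point. The regression sentence does not commit to stage, and because it follows the repeated-measures text on the RAS markers, it is unclear whether it covers RP and fibrosis at all. The possible loss is negligible when strata are few, which the SAP can fix in advance.

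**Conclusion.** The concern holds as a near-free improvement to the plan. The deciding test for RP and fibrosis does not use the only factor that randomisation controls, while the Aim 3 model does. Type I error is not inflated.

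For clinical RP at 11% cut by 80%, the expected power gain runs from nil if stage is weakly related to RP to about 3 points if the gradient is steep and the test two-sided. It is 1.3 to 1.6 points for 20% halved at 10/30%, at most 1.4 points for radiographic RP, and nil for fibrosis. These figures rest on assumed stage rates, two strata and 100 analysable subjects per arm. Naming one stage-adjusted analysis in advance also settles which RP result decides, whatever the power gain. The change should be made.

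**What to change.** In the SAP section on endpoint analyses, state that:

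- the deciding analysis for clinical RP, radiographic RP and fibrosis is a CMH test stratified by the stage groups used at randomisation, or a logistic model with treatment and stage, reported with a common effect estimate and 95% confidence interval;
- the unadjusted chi-square or Fisher test is supportive;
- if the randomisation strata are many, they are collapsed to a few broad stage groups fixed before unblinding, and those groups are the CMH strata.

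The last item matters because about 13 clinical RP events cannot support many strata. The cost is one or two sentences of SAP text. Stage is already recorded for randomisation, so no new data are needed. With two balanced strata nothing is lost if stage turns out not to matter; under simple allocation the loss is about 0.5 points or less.
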